9.3.2. Outcome identification algorithms

The primary HOIs are GBS, gout, PMR, and GCA. Secondary HOIs are SVT and ION. Table 3 describes the case definition algorithm for the primary and secondary HOIs, which also details the sensitivity analyses where validated outcome identification algorithms are not available in the literature for reference.

- All algorithms use medical claims from the inpatient, outpatient or carrier claim files and are based on the ICD-10 codes.
- An inpatient claim is defined as a claim generated from an admission to a hospital.
- An ED (Emergency Department) visit is defined as a claim generated from a visit to an urgent care unit within a hospital, but it is not a hospital admission.
- An outpatient claim is defined as a claim generated by a visit to a provider in an ambulatory practice setting, e.g., physician office, health clinic.
- For algorithms that require ≥ 2 claims, the date of the first claim will define the first occurrence of the HOI. The two claims must occur within the designated follow-up interval.
- For the SCRI design, new onset of the HOI, i.e., incident case, is determined based on the first occurrence and no record of the HOI in the preceding 365 days.
- For the cohort design, new onset of the HOI, i.e., incident case, is determined based on the first occurrence after the index date (i.e., RZV vaccination or the preventive care visit date for RZV unvaccinated comparators) and no record of the HOI in the 365 days preceding the index date (i.e., baseline period).
- For GBS, the earliest onset date is the hospitalization date for claims in the inpatient setting or the earlier GBS claim when the diagnosis occurs in any setting followed by an inpatient claim within 7 days.

Table 3HOI case identification algorithms

1	2	3	4	5	6	7	8	9	10
Study Outcome (Study design)	ICD-10 code(s) for case ascertainment	Validation Statistics	Other requirements ^c	Setting for case ascertainment	Risk Interval	Look-back period & settings to determine incidence	What to look back for	What to look back from	Sensitivity Analysis
GBS (SCRI)	G61.0	PPV: 50% (Inpatient visit) ¹⁴	None	Inpatient primary position OR Diagnosis in any setting followed by an inpatient claim within 7 days	Days 1-42	1 year; inpatient; primary position only	Same as in Col.2	HOI	N/A

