209696 (EPI-ZOSTER-032 VS US DB)

Protocol Amendment 3 Final

1	2	3	4	5	6	7	8	9	10
Study Outcome (Study design)	ICD-10 code(s) for case ascertainment	Validation Statistics	Other requirements ^c	Setting for case ascertainment	Risk Interval	Look-back period & settings to determine incidence	What to look back for	What to look back from	Sensitivity Analysis
ION (Cohort)	H47.01	Not available	Exclude patients who had coronary artery bypass graft (CABG) surgery ¹⁷ or lumbar or lumbosacral spinal fusion and/or laminectomy surgery within 30 days before ION diagnosis date	≥1 claim in all settings	Days 1-183	1 year; all settings ^b ICD code only	Same as in Col. 2	Exposure	Additional criteria for arteritic: ≥ 40 mg/day of prednisone prescription ± 4 weeks of the diagnosis plus an ophthalmologist/neuro- ophthalmologist consult (if possible) and GCA diagnosis within 3 months; lookback to rule out prevalent cases will use ICD code only; all settings
SVT (SCRI)	147.1	Sensitivity-91.7% ¹⁸	None	≥1 ED or inpatient claim any position	Days 1-30	1 year; all settings ^b any position	Same as in Col. 2	HOI	N/A

Definitions: ALS - Amyotrophic Lateral Sclerosis; CVA - Cerebrovascular Accident; GCA - Giant Cell Arteritis; GSB - Guillain-Barré Syndrome; ION - Ischemic Optic Neuropathy; PMR - Polymyalgia Rheumatica; SCRI - Self-controlled Risk Interval; SVT - Supraventricular Tachycardia;

^a Outpatient visits are defined using ≥2 claims for consistency with methods used by CMS algorithms using the CMS CCW Medicare data to define chronic conditions, and to avoid misclassification of the outcome due to the potential for 1 visit to reflect rule-out diagnosis.

^b Includes inpatient, emergency department, and outpatient settings.

^c Based on external expert opinion.

^d Consistent with the study EPI-ZOSTER-030 VS US DB, no analysis will be conducted for the gout sensitivity HOI definitions. These definitions are for administrative purposes only .

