9.7.6. Inferential analyses for the primary outcomes (*Amended 15 July 2022*)

An overview of the planned primary, secondary, and sensitivity analyses were presented earlier in Table 1. Details of the analysis are described here.

- GBS and gout will be analyzed using a SCRI design
- PMR and GCA will be analyzed using a cohort design

Analysis of the SCRI Design

Additional inclusion requirements for the SCRI design analyses for new onset (i.e., incidence) primary HOIs GBS and gout include:

- 1. Receipt of RZV vaccination;
- 2. First occurrence in a 365-day look-back from the HOI in the risk or control interval;
- 3. Continuously enrolled in Medicare Parts A, B, and D fee-for-service for at least 365 days preceding the date of RZV vaccination. Continuous enrollment is determined by Medicare enrollment in the month of the RZV vaccination and enrollment in at least 11 of the 12 preceding months.
- 4. *Continuous* enrollment in Parts A and B (and in the case of gout Part D to capture gout-specific medication) through the end of the respective control interval.

The use of a first-in-365-days definition of HOI incidence is important and customary with the SCRI design to establish an equal opportunity for a case to be ascertained regardless of where in the follow-up (risk and control) period it might appear. The enrollment requirement for the defined amount of follow-up time, i.e., through the end of the control interval, will exclude people who die or lose eligibility before that time. However, because the HOIs addressed in this study are usually not fatal, we do not expect this requirement to produce any appreciable bias in our analyses. Moreover, the follow-up time (risk and control) is relatively short (84 and 60 days for GBS and gout, respectively), and we do not expect exclusion due to death would impact many individuals. In the relatively short follow-up time, we also do not anticipate loss of eligibility will produce appreciable bias in the analyses.

Per US schedule, RZV is indicated as a two-dose schedule, 2 to 6 months apart, thus it is not possible to define a consistent control interval for Dose 1. The control interval following Dose 1 may overlap with the risk interval following Dose 2. Therefore, the control interval following Dose 1 will depend upon the time between doses. The potential scenarios are illustrated in Figure 1.

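### The GBS look-back in Table 3 is narrower than the GBS case definition and conflicts with the new-onset rules in 9.3.2 and 9.7.6, so pre-existing GBS can be counted as new onset

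*Combined protocol and SAP*

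**What the plan says.** Section 9.3.2 states the SCRI rule for an incident case: a first occurrence with "no record of the HOI in the preceding 365 days". Section 9.7.6 repeats it as an inclusion requirement: "First occurrence in a 365-day look-back from the HOI in the risk or control interval". Neither limits the setting or the diagnosis position.

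The GBS row of Table 3 makes this operational. Cases are found by "Inpatient primary position OR Diagnosis in any setting followed by an inpatient claim within 7 days". The look-back runs from the HOI, searches for G61.0, and is limited to "1 year; inpatient; primary position only". The sensitivity-analysis cell for GBS is N/A.

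For gout, PMR, GCA, ION and SVT the same column specifies all settings, which footnote b explains: "Includes inpatient, emergency department, and outpatient settings". The SVT row adds that any position counts.

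Section 9.3.2 dates GBS at the hospitalization date or, on the any-setting route, at the earlier GBS claim.

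**The concern.** The screen for earlier disease is narrower than the route by which new cases enter. Applied as Table 3 is written, it leaves two gaps.

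- **Earlier GBS seen only outside a primary-position admission.** Someone with prior-year G61.0 codes in outpatient, emergency, carrier or secondary inpatient positions passes the look-back. A later visit coded G61.0, with an inpatient claim within 7 days, makes that person a new case. Table 3 does not say that the inpatient claim must itself carry G61.0.
- **GBS first coded before vaccination.** If the primary-position admission follows the clinic code by more than 7 days, onset is dated to the admission, which can fall in the risk window.

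GBS is a primary outcome, and section 7 cites a post-licensure signal for it. Charts cannot be reviewed (9.4.2, 9.9). The dose-spacing, seasonality and COVID-19 analyses do not change the GBS case definition, so none of them would show the effect.

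**Working it through.** **1. Text set side by side**

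| Place | Settings | Position |
|---|---|---|
| 9.3.2, SCRI new-onset rule | not limited | not limited |
| 9.7.6, SCRI inclusion item 2 | not limited | not limited |
| Table 3, GBS ascertainment | inpatient, or any setting plus inpatient claim within 7 days | primary on the inpatient route; not limited on the any-setting route |
| Table 3, GBS look-back | inpatient | primary only |
| Table 3, look-back for the other five outcomes | all | any, for SVT; not limited for the rest |

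The GBS look-back is the only entry that cannot see a code which the GBS ascertainment rule can accept.

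**2. The plan's own GBS figure**

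Inputs from 9.5.2, Table 4 and 9.7: RR 4, two-sided alpha 0.05, power 80%, 2 per 100,000 person-years, mean control window 36 days. I used the signed-root likelihood-ratio formula for self-controlled case series, with r the risk-window share of follow-up:

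- A = 2[ρr·ln ρ/(ρr+1−r) − ln(ρr+1−r)]
- B = (ln ρ)²/A × ρr(1−r)/(ρr+1−r)²
- n = (1.96 + 0.8416√B)²/A

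At ρ = 4 and r = 0.5, A = 0.3855 and B = 0.7977, so n = 19.07. With r = 42/78, n = 20.23. The plan states 20.

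Control-window cases: 20/(4+1) = 4. Vaccinations: 4/0.197125 × 100,000 = 2,029,167, or 1,014,583 people at two doses each. The plan states 2,000,000 and 1,000,000. The sample-size figure reproduces and is not in question.

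**3. Pull toward 1**

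Let f be the share of counted cases that are prevalent. The documents give no value, so f is assumed. With equal windows, an even split of prevalent cases and a true IRR of 4, the risk-window proportion is p = 0.8(1−f) + 0.5f and the observed IRR is p/(1−p). Power at n counted events is Φ[(√(nA) − 1.96)/√B], with A and B taken at the observed IRR.

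| f | p | Observed IRR | Power at 20 counted events |
|---|---|---|---|
| 0 | 0.800 | 4.00 | 82% |
| 5% | 0.785 | 3.65 | 77% |
| 10% | 0.770 | 3.35 | 72% |
| 20% | 0.740 | 2.85 | 60% |

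**4. Push upward**

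Twenty events at IRR 4 are 16 in the risk window and 4 in the control window. One pre-vaccination case landing in the risk window gives 17/4 = 4.25. One prevalent case landing in the control window gives 16/5 = 3.2. The two gaps work in opposite directions.

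**5. Projected study size**

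Section 9.2.2 projects a little more than 2 million eligible vaccinees. At two doses each, 4,000,000 × 0.197125/100,000 = 7.9 control-window cases. At RR 4 that is 7.9 × 5, or about 39 events. If prevalent cases replace true ones within 39 counted events, power at f = 10%, 20% and 30% is 95%, 88% and 77%. If they are added to 39 true events, it is 97%, 94% and 90%.

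**The case against.** The strongest reply is that this may be a wording conflict only. If the prose of 9.3.2 and 9.7.6 governs, any earlier G61.0 code excludes the person and there is no gap. That is possible, but Table 3 is the operational definition, it is explicit, and nothing says that the prose overrides it. The passages need reconciling on either reading.

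The gap is also narrow. A primary-position GBS admission in the prior year is already excluded, and the any-setting route still needs an inpatient claim within 7 days. This stands: such cases can be counted, but nothing shows how many will be.

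A reader might go further and infer that prevalent GBS does dilute the IRR and that the study will lose a true signal. The documents do not support that. The prevalent share is not given, the second gap acts upward, and the power losses in step 3 belong to the 20-event minimum. At the projected size, power for RR 4 stays at or above 88% with up to 20% contamination. Bias in the IRR for a given share does not shrink with sample size, however.

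Finally, a wider look-back has a cost. Footnote a of Table 3 recognises that a single outpatient visit may be a rule-out diagnosis, so one such code could remove a true case. That stands as a downside, but the protocol does not offer it as the reason for the narrow GBS rule and accepts the same risk in the all-settings look-backs for the other outcomes.

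**Conclusion.** The inconsistency is established from the text: the GBS look-back in Table 3 does not implement the new-onset rule in 9.3.2 and 9.7.6, is narrower than its own ascertainment rule, and differs from every other outcome without a stated reason. Followed as written, it can admit pre-existing or pre-vaccination GBS as new onset for a primary outcome.

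The size is conditional. An observed IRR of 3.65, 3.35 or 2.85 for a true 4 rests on assumed prevalent shares of 5%, 10% and 20%, equal windows, and prevalent claims unrelated to time since vaccination. Pre-vaccination disease reaching the early risk days would raise the IRR. The net direction cannot be determined from the documents. The point merits correction before analysis because the effect is unmeasured, no planned analysis would reveal it, and the change is small.

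**What to change.** In the GBS row of Table 3, set the look-back to G61.0 in all settings and any diagnosis position, over the 365 days ending the day before the HOI date. Keep the HOI date as 9.3.2 already defines it (hospitalization date or, on the any-setting route, the date of the GBS diagnosis that precedes the inpatient claim), so that a case's own qualifying claim does not exclude it. Leave the 7-day onset rule unchanged: moving onset back to the earliest code in any setting would retain the same patient whom the wider look-back excludes.

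Report the number of cases removed, separately for risk and control windows. Replace the N/A in the GBS sensitivity cell with the present inpatient primary-position look-back, and report the IRR under both. Section 10 suppresses table cells below 11, so where the counts by window are too small to show, the two IRRs carry the comparison.

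The cost is a changed filter on claims already to be obtained, plus one extra run. Some true incident cases will be lost: those with an earlier rule-out code, and those first coded in clinic more than 7 days before admission. The documents do not allow that loss to be estimated, but the sensitivity analysis will show its effect.

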Gout (SCRI)	M10.x, M1A.x (chronic gout)	PPV: 61% (≥ 2 visits associated with the diagnosis) ¹⁵	At least one gout- specific oral medication (allopurinol, colchicine, probenecid, febuxostat) prescribed within 3 months after the first date of the diagnosis.	≥2 outpatient claims within the follow-up windowa OR ≥1 inpatient claim	Days 1-30	1 year; diagnosis code –all settings ^b OR At least one gout- specific oral medication (allopurinol, colchicine, probenecid, febuxostat);	Same as in Col. 2 OR Col. 4	HOI	-Exclude chronic and secondary gout codes. -Examine frequency distribution of ICD-10 codes and consider low- frequency codes such as codes for chronic gout (M1A*), lead- induced gout (M10.1*, drug-induced gout (M10.2*), and gout due to renal impairment (M10.3*) (note: this exclusion of gout codes does not apply in assessing prevalent gout) ^d

209696 (EPI-ZOSTER-032 VS US DB) Protocol Amendment 3 Final

1	2	3	4	5	6	7	8	9	10
Study Outcome (Study design)	ICD-10 code(s) for case ascertainment	Validation Statistics	Other requirements ^c	Setting for case ascertainment	Risk Interval	Look-back period & settings to determine incidence	What to look back for	What to look back from	Sensitivity Analysis
PMR (Cohort)	M35.3 – PMR M31.5 – GCA w/ PMR	Sensitivity: 99.5% Specificity: 92.2% ¹⁶ (based on the 3 methods used by Bernatsky: diagnosis in inpatient or outpatient, or a visit by a rheumatologist/ internist)	2 oral glucocorticoids (cortisone, dexamethasone, hydrocortisone, methylprednisolone, prednisolone, prednisone) prescriptions; The first dispensing within 6 months of PMR diagnosis and the second dispensing date within 6 months after the first dispensing.	≥2 outpatient claims within the follow up window a OR ≥1 inpatient claim	Days 1-183	1 year; all settings⁵	Same as in Col. 2	Exposure	N/A
GCA (Cohort)	M31.6 (GCA), M31.5 (GCA with PMR), M31.9 (necrotizing vasculopathy unspecified)	Not available	2 oral glucocorticoids (cortisone, dexamethasone, hydrocortisone, methylprednisolone, prednisolone, prednisone). The first dispensing within 6 months of GCA diagnosis and the second dispensing date within 6 months after the first dispensing.	≥2 outpatient claims within the follow up windowª OR ≥1 inpatient claim	Days 1-183	1 year; all settings⁵	Same as in Col. 2	Exposure	-Use the primary algorithm based on the GCA diagnosis code and steroid prescription but ADD a requirement for a temporal artery biopsy at the time of diagnosis, as determined by a CPT code=37609

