9.7. Data analysis

- All the statistical analyses will be done in SAS 9.4.
- All the statistical tests will be two-sided at alpha level of 0.05.
- All 95% CIs will be estimated as the point estimate ± 1.96 *standard error.

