The primary analysis will assess each dose separately and will yield two separate risk estimates for Dose 1 and Dose 2. Exposure is defined as at least one dose of the RZV vaccine. The risk period for the cohort analysis is 183 days from index date. The index dates are Doses 1 and 2 is the vaccination date for the RZV cohort and preventive care visit date for the RZV unvaccinated cohort. The scenarios for the primary analysis are illustrated in Figure 2.

Figure 2 Cohort Design: Primary analysis with separate Dose 1 and Dose 2 analysis

Secondary analyses of the cohort design.

The secondary analyses will combine Dose 1 and Dose 2.

- One risk estimate: This secondary analysis of combined doses does not distinguish between doses to yield one risk estimate.
- Two separate risk estimates: An additional secondary analysis combines Dose 1 and Dose 2 in the same analytic model but yields two separate risk estimates.

All individuals will be followed up for 183 days from the Dose 1. The maximum allowable spacing between doses will be 365 days. This means that Dose 2 is not included in the analysis if it is received more than 365 days after Dose 1. We anticipate the majority of individuals will receive Dose 2 within 365 days. RZV vaccinated individuals may have up to two measures (i.e., one for Dose 1 and one for Dose 2). The RZV unvaccinated comparators similarly will have up to two measures for the index dates for preventive care visits. Robust variance estimators will be used to account for repeated measures on the same individual.

Sensitivity analysis of the cohort design.

• Dose compliant analysis: The sensitivity analysis is restricted to the sub-sample that received Dose 1 and Dose 2 per US dosing schedule, i.e., 2-6 months apart. Analysis will be conducted similar to the secondary analysis (i.e combined doses yielding a single risk estimate and separate doses yielding two risk estimates).

Sensitivity analysis of alternative definition of GCA

• The number of cases and the incidence rate (or cumulative incidence) among vaccinated and preventative care comparators who are identifed using the sensitivity analysis HOI definition of GCA (Table 3 Column 10) will be reported. Futher analysis consistent with the primary (1°) analysis for the cohort design (i.e. analysis of separate doses) will be conducted, if an appropriate number of cases are identified to allow meaningful inference.

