Case ascertainment. It will not be possible to conduct a chart review to validate HOIs. Case-finding algorithms using administrative data are rarely sensitive and specific. The algorithms used in this study are found to have high positive predictive value in published case validation studies and we consulted with experts.

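### The primary GCA definition accepts an unspecified vasculopathy code (M31.9), and no planned analysis estimates the hazard ratio on GCA-specific codes alone

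*Combined protocol and SAP*

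**What the plan says.** Section 9.3.2, Table 3, GCA row, lists the case codes as "M31.6 (GCA), M31.5 (GCA with PMR), M31.9 (necrotizing vasculopathy unspecified"). A case needs at least two outpatient claims in the follow-up window or at least one inpatient claim, plus two oral glucocorticoid prescriptions: "The first dispensing within 6 months of GCA diagnosis and the second dispensing date within 6 months after the first dispensing". The validation entry is "Not available". The one-year look-back covers all settings and uses the same codes, so an M31.9 record in the year before the index date excludes the person.

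The only alternative GCA definition is in Column 10: "Use the primary algorithm based on the GCA diagnosis code and steroid prescription but ADD a requirement for a temporal artery biopsy", identified by a single CPT code. Section 9.7.6 says that case numbers and incidence under this definition will be reported for both arms. Modelling follows only "if an appropriate number of cases are identified to allow meaningful inference".

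Section 9.9, under case ascertainment, says: "The algorithms used in this study are found to have high positive predictive value in published case validation studies".

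**The concern.** Two of the three codes name GCA. The third, by the plan's own label, does not. Nothing in the row requires any qualifying claim to carry one of the two GCA codes, so M31.9 alone is enough.

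The steroid requirement does little to separate the conditions. The polymyalgia rheumatica row uses the same drug list and the same two-dispensing rule, so the rule marks steroid treatment and not GCA in particular. The footnote citing external expert opinion is attached to the column holding the steroid rule, not to the code list. No reason for including M31.9 is given.

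GCA is a rare primary outcome. It is studied because of 6 cases against 3 in the pooled trials (Section 7). If an unknown part of the counted cases is some other vasculitis, neither a null nor a raised HR can be read as a statement about GCA, and the planned analyses would not show how far the result depends on M31.9.

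**Working it through.** **1. Is M31.9 removed anywhere?**
- Primary definition: M31.6, M31.5 or M31.9, with two steroid dispensings.
- Biopsy definition: the primary algorithm plus a biopsy code, so M31.9 stays.
- Secondary, dose-compliant, COVID-19 and supplemental analyses (Sections 9.7.6, 9.7.8, 9.7.9): none states a different GCA code list.

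No analysis uses M31.6 and M31.5 alone.

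**2. Reproducing the plan's sample size.** Inputs from Section 9.5.2 and Table 5: baseline b = 0.000092, exposed share π = 0.2 (1:4), T = 0.5 year, two-sided alpha 0.05, power 80%, RR 3. The Poisson-regression formula for a binary exposure is

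N = [z(0.975)·√V0 + z(0.80)·√V1]² / (b·T·(ln RR)²), with V0 = 1/(π(1−π)) and V1 = 1/(1−π) + 1/(π·RR).

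- V0 = 1/(0.2 × 0.8) = 6.25
- V1 = 1.25 + 1.667 = 2.917
- N = (1.960 × 2.5 + 0.842 × 1.708)² / (0.000046 × 1.207) ≈ 723,361, against 723,362 stated

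The formula matches every row of Table 5 to within one person. The table contains no arithmetic error.

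**3. Effect on the HR.** Let f be the share of comparator-group algorithm cases that enter through M31.9 and are not GCA. Then

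observed HR = (1−f)·HR(GCA) + f·HR(other).

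With HR(other) = 1 this becomes 1 + (1−f)(HR−1). The values of f are assumptions.

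| Scenario | f = 10% | f = 25% | f = 50% |
|---|---|---|---|
| GCA HR 3, other HR 1 | 2.8 | 2.5 | 2.0 |
| GCA HR 3, other HR 3 | 3.0 | 3.0 | 3.0 |
| GCA HR 1, other HR 2 | 1.1 | 1.25 | 1.5 |
| GCA HR 1, other HR 1 | 1.0 | 1.0 | 1.0 |

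The first row is attenuation. The third is a raised GCA estimate with no GCA effect.

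**4. Effect on sample size** (true GCA HR 3, other HR 1, 80% power). The answer depends on whether 0.000092 already includes the non-GCA cases, which Section 9.5.2 does not say. If they come on top, the baseline is 0.000092/(1−f), and the required N is (1−f) times the first figure.

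| f | Observed HR | N if 0.000092 includes them | N if they add to it |
|---|---|---|---|
| 10% | 2.8 | 831,117 | 748,005 |
| 25% | 2.5 | 1,066,257 | 0.75 × 1,066,257 ≈ 799,693 |
| 50% | 2.0 | 1,929,204 | 0.5 × 1,929,204 = 964,602 |

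Section 9.2.2 projects about 2 million exposed and 8 million comparators, or 10 million in total, which is well above every entry. At that size, power for a true HR of 2 is still about 96% at f = 50% in the less favourable case. The smallest true HR detectable with 80% power moves from 1.37 at f = 0 to 1.74 (included) or 1.50 (added) at f = 50%.

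**The case against.** Four points can fairly be made for the plan.

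- **Other filters limit f.** Two outpatient claims or an admission, two steroid dispensings, and a one-year look-back on the same codes all reduce stray coding and recorded prevalent disease. This stands, and f may be small. But these filters do not turn an unspecified vasculopathy into GCA, and the plan reports nothing that would reveal f.
- **A specificity check exists.** The biopsy definition is aimed at GCA, and its counts and incidence are reported whatever the numbers; only the modelling is conditional. This also stands. The definition still admits M31.9, however, and a procedure code shows that a biopsy was done, not what it found.
- **Code breadth is a trade-off.** Some M31.9 cases may be true GCA, and nothing in the documents shows that the two-code list must be primary. This is right, and it is why the request is for an added analysis.
- **The plan is open about its limits.** Section 9.9 says that claims algorithms are rarely sensitive and specific and that charts cannot be reviewed.

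A reader might go further and infer that M31.9 pulls the HR toward 1 and so hides harm. The documents do not establish this. It requires a true GCA HR different from 1 and other vasculitis that the vaccine does not affect, and neither is shown. A reader might also set the Table 5 sizes for RR 2.5 and 2.0 against 723,362 and infer that the GCA analysis is underpowered. That comparison takes the less favourable reading of the baseline and ignores the projected 10 million people.

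**Conclusion.** The point holds as a matter of what the GCA hazard ratio estimates. A person coded only M31.9 is a primary GCA case, the algorithm has no validation statistics, and no planned analysis isolates the GCA-specific codes. If the non-GCA cases are unrelated to the vaccine, a true HR of 3.0 reads between 2.8 and 2.0 for f between 10% and 50%. That range is illustrative, since f cannot be derived from the documents, and under other assumptions the bias is nil or runs away from 1. Detection of the stated target of 3 is not in doubt at the projected size, but a larger sample does not remove this bias. Dropping M31.9 brings f, as defined here, to zero; it does not remove false cases that arise within M31.6 or M31.5.

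Separately, the general claim of high positive predictive value in Section 9.9 does not fit the GCA row of Table 3, which has no validation figure to support it.

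**What to change.** In Table 3 Column 10 and Section 9.7.6:

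1. Prespecify a Cox analysis of GCA restricted to M31.6 and M31.5, following the primary separate-dose analysis and not conditional on case numbers. Keep M31.9 in the one-year look-back. Column 10 already takes this approach for the gout codes, although a footnote says those gout definitions will not be analysed.
2. Report GCA cases by code and by arm, subject to the small-cell suppression rule in Section 10.
3. Run the biopsy definition on the two GCA codes as well.
4. Give the reason for including M31.9, and state in Section 9.5.2 whether the 0.000092 baseline includes it.
5. Reconcile the Section 9.9 statement on predictive value with the GCA row of Table 3.

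The sponsor may choose to make the two-code definition primary and the three-code one the sensitivity analysis. Either way, the choice should be fixed before GCA results by arm are seen.

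The cost is a protocol amendment and one more run of an existing model on data already planned. The two-code analysis loses any true GCA cases coded only as M31.9. Their number is unknown, and the counts by code will show at most how many there could be.
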